Enter user name: uabmcD0

Password: BU6007

Click Reports, select start and end date and click 'generate'.

D. Alcohol Pharmacotherapy (APT)

During visit 1, participants who have scored AUD on MINI would become eligible to receive Alcohol Pharmacotherapy (APT).

Providers/PCC/study staff can call/page [name]/ [name] in case they have questions on medications.

Information for [name]:

- ✓ [contact]
- ✓ [contact]
- ✓ Email: [contact]

Information for [name]:

- ✓ [contact]
- ✓ [contact]
- ✓ Email: [contact]

In instances where you cannot reach them by phone and need to leave a VM.

VM to leave: *Hi this is 'XYZ', I have a question on ARCH IRA participant who is in the clinic/ or not in the clinic (use as appropriate). Please call back at 'phone number'.*

Paging instructions:

- Go to <https://www.paging.uab.edu/>
- Enter the last 4 digits of the pager number or name in the box and click search. You will see name and pager number that pops up.
- Click the pager number which is bold and green and a screen will come up saying enter your message and send button. You can only enter 80 characters for message.
- Enter message and click hit send.
- Message to send: *Question on ARCH IRA participant. Call back on 'phone number'.*

i. UAB

Study staff/PCC will use the APT algorithm ([Appendix 1 Algorithm 2](#)) and the EMR to determine which medication to recommend to the provider. Study staff/PCC will communicate with participant's provider in clinic and/or send a message through the EMR and recommend a drug from the APT list. These recommendations will be done based on APT algorithm plus consultation with PI ([name]) of the study/addiction specialist ([name] [name]) on case-

by-case basis via email or phone communication. Template scripts of these recommendations can be found in **Appendix XX**.

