If APT is prescribed to the participant, study staff/PCC will communicate with participant about the side effects of the recommended drug (described in Appendix 2 under medication list) and make sure that the participant understands to call study staff/PCC and clinical care team in case s/he experiences any side effects. In addition, study staff/PCC will follow up with participants in one week to see how they are doing on their medication. Attempts will be made up to one month following receipt of medication. Study staff/PCC will call twice per week in attempting to reach the participant. If participant reports a side effect, the study staff/PCC will inform the participant's clinical care team using message center in the Cerner. The provider will determine the course of action to be taken (e.g., continue, reduce dose, and discontinue medication). [name]/ [name] will be available for provider to consult about medication.

ii. UW

A similar set of procedures will be used for most of these steps at the UW.

Providers will receive a notification for patients eligible for APT:

XX is participating in the ARCH-IRA study and reported at-risk alcohol use on the clinical assessment. Based on XX's risk, he is eligible and would likely benefit from Alcohol Pharmacotherapy (APT). Naltrexone is most often recommended for APT unless the patient has acute hepatitis or liver failure (LFTs>5x ULN) or is currently using prescribed or illicit opioids. The dose of naltrexone is 50 mg PO per day. We have attached an APT medication algorithm and list of medications and doses for your information. We hope this information is useful to you and that you consider whether prescribing APT would be of benefit to George.

At UW, this message can be sent through Epic with algorithm attached or printed and handed directly to provider. The assessment of appropriateness of specific APT choices based on LFTs or opiate use will be assessed by and at the discretion of the patient provider. The PCC will contact participants as above and address issues with participant regarding access, receipt of, and other issues with APT but side effects will be deferred to clinical staff.

iii. UCSD

TBD

iv. JHU

TBD

E. Dried Blood Spots

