Vivitrol (PO naltrexone)	Tablet	50 mg 1x/day with food	
Common side effects: nausea, vomiting, stomach pain, diarrhea, constipation, loss of appetite, headache, dizziness, anxiety, nervousness, irritability, tearfulness, difficulty sleeping, increased or decreased energy, drowsiness, muscle or joint pain, rash
 
More serious side effects: confusion, hallucinations, blurred vision, severe vomiting and/or diarrhea

Opioid list as prescribed in Cerner at UAB

Opiates
acetaminophen/butalbital/caffeine/codeine
acetaminophen-codeine
acetaminophen-HYDROcodone
acetaminophen-oxycodone
acetaminophen-tramadol
APAP/butalbital/caffeine/codeine
APAP/caffeine/dihydrocodeine
aspirin/butalbital/caffeine/codeine
aspirin-oxycodone
bupivacaine-fentanyl 200 mL
bupivacaine-fentanyl 250 mL
bupivacaine-HYDROMorphone 250 mL
buprenorphine
buprenorphine-naloxone
butorphanol
chlorpheniramine/hydrocodone/phenylephri
chlorpheniramine/hydrocodone/phenylephrine
chlorpheniramine-hydrocodone
codeine
codeine/guaifenesin/PSE
codeine/guaiFENesin/pseudoephedrine
codeine/phenylephrine/promethazine
codeine-guaifenesin
codeine-promethazine
dexbrompheniramine/hydrocodone/phenyleph
dexbrompheniramine/hydrocodone/phenylephrine
dihydrocodeine/guaiFENesin/phenylephrine
diphenhydramine/hydrocodone/phenylephrine
fentanyl
fentanyl 1
fentanyl 1,000 mcg [0.5 mcg/kg/hr] + dex
fentaNYL 2
fentaNYL 2,500 mcg [100 mcg/hr] + empty
fentaNYL 2,500 mcg [100 mcg/hr] + empty sterile container for IV fluids 50 mL
fentanyl 2,500 mcg [200 mcg/hr] + empty
fentaNYL 2,500 mcg [25 mcg/hr] + empty s
fentaNYL 2,500 mcg [25 mcg/hr] + empty sterile container for IV fluids 50 mL

fentaNYL 2,500 mcg [50 mcg/hr] + empty sterile container for IV fluids 50 mL
fentanyl 2,500 mcg [75 mcg/hr] + empty s
fentanyl 2,500 mcg [75 mcg/hr] + empty sterile container for IV fluids 50 mL
fentanyl 2500 mcg + empty sterile contai
fentaNYL 5
fentaNYL 5,000 mcg [1 mcg/hr] + empty st
fentaNYL 5,000 mcg [1 mcg/hr] + empty sterile container for IV fluids 100 mL
fentaNYL 5,000 mcg [10 mcg/hr] + empty sterile container for IV fluids 100 mL
fentaNYL 5,000 mcg [100 mcg/hr] + empty
fentaNYL 5,000 mcg [100 mcg/hr] + empty sterile container for IV fluids 100 mL
fentaNYL 5,000 mcg [150 mcg/hr] + empty
fentaNYL 5,000 mcg [150 mcg/hr] + empty sterile container for IV fluids 100 mL
fentaNYL 5,000 mcg [200 mcg/hr] + empty
fentaNYL 5,000 mcg [200 mcg/hr] + empty sterile container for IV fluids 100 mL
fentanyl 5,000 mcg [25 mcg/hr] + empty s

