fentaNYL 5,000 mcg [25 mcg/hr] + empty sterile container for IV fluids 100 mL
fentanyl 5,000 mcg [50 mcg/hr] + empty s
fentaNYL 5,000 mcg [50 mcg/hr] + empty sterile container for IV fluids 100 mL
fentanyl 5,000 mcg [75 mcg/hr] + empty s
fentanyl 5,000 mcg [75 mcg/hr] + empty sterile container for IV fluids 100 mL
fentanyl 5000 mcg [50 mcg/hr] + dextrose
fentanyl-ropivacaine 250 mL
guaifenesin/hydrocodone/phenylephrine
guaifenesin-hydrocodone
homatropine-hydrocodone
HYDROcodone
HYDROcodone/phenylephrine/pyrilamine
hydrocodone-ibuprofen
hydrocodone-pseudoephedrine
HYDROMorphone
ibuprofen-oxycodone
meperidine
meperidine-promethazine
methadone
morphine
morphine 250 mg [1 mg/hr] + Diluent for
morphine 250 mg [2 mg/hr] + Diluent for
morphine 30 mg [2 mg/hr] + Diluent for P
morphine-naltrexone
nalbuphine

opium
oxycodone
oxymorphone
tapentadol
traMADol
fentaNYL 5,000 mcg [100 mcg/hr] + Diluent for Premix 100 mL
fentaNYL 5,000 mcg [150 mcg/hr] + Diluent for Premix 100 mL
fentaNYL 5000 mcg [150 mcg/hr] + Diluent for Premix 100 mL
guaiFENesin/HYDROcodone/pseudoephedrine
Paregoric Liquid
Acetaminophen; Tramadol
acetaminophen-hydrocodone
buprenorphine
codeine syrup 5mg/ml
Duragesic patch
HYDROCO/APAP
hydrocodon 10/500
Hydrocodone
hydrocodone 10mg
Hydrocodone 10mg - 325 mg
loratab
Lortab
Lortab 7.5 mg
methadone
methadone 100 mg daily
morphine
morphine sulfate
ms contin 300mg every 8 h
Norco
Norco 7.5mg/325mg
Norco oral four times a
Opium Tincture
Paregoric Liquid
percocet does unknown
Suboxone Troche
tramadol 325mg-37.5mg tid
Tussionex
Tussionex tablets
Virtussin
Hydrocodone-Apap 10/500mg every 4hr prn

lortab

Morphine-sul er 60 mg 3 tabs BID

tylenol #4 taken as
needed

Medications Containing Alcohol

MEDICATIONS CONTAINING ALCOHOL COMMONLY STOCKED IN MOST HOSPITALS AND PHARMACIES

Drug	% Alcohol	Drug	% Alcohol	Drug	% Alcohol
Actol Expectorant Syrup	12.5	Feosol Elixir	5.0	Phenergan Expectorant VC Plain	7.0
Alertonic	0.45	Fer-In-Sol Syrup	5.0	Phenergan Expectorant VC	
Alurate Elixir	20.0	Theoelixir (Elixir Theophylline)	20.0	w/Codeine	7.0
Ambenyl Expectorant	5.0	Elixophy	20.0	Phenergan Expectorant Pediatric	7.0
Anahist	0.5	Elixophylline-KL	10.0	Phenergan Syrup Fortis (25 mg)	1.5
Aromatic Elixir	22.0	Ephedrine Sulfate Syrup USP	3.0	Polaramine Expectorant	7.2
Anaspaz-Pb Liquid	15.0	Ephedrine Sulfate Syrup -		P.B.Z. Expectorant with Ephedrine	6.0
Asbron Elixir	15.0	Note USP	12.0	Propadrine Elixir HCl	16.0

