When you have finished a topic, click on the “Back to Topics Selection page” link at the top of the page. From there, you can choose the next topic from the middle of the page, or from the “Recommended Order” list on the left of the page.

I am not sure what to do for this activity.

For each activity, a short explanation will play before you begin. If you missed this explanation or would like to hear it again, click on the “Restart Page” button at the bottom of the page.

The program has me watch the same video several times.

While there are many videos in the program that are similar, there are small differences between each one. These differences may include changes to what people say, how they behave in different situations, or what they are thinking. Pay close attention to these differences, as they are usually there to show how changing your behaviors can change the situation.

Appendix 5

APT scripts template at UAB for these recommendations will be:

Message to Fellow/Nurse Practitioner CC Attending, [name], [name], [name], in IMPACT Message Center: INTERVENTION PARTICIPANTS

If Naltrexone Prescription

Subject: ARCH IRA study

Pt enrolled to ARCH IRA study: U01 AA020802 - Alcohol Research Consortium on HIV – Intervention Research Consortium

Enrolled on xx/xx/yyyy, with a AUDIT/AUDIT C score of XX

Patient name scored >=4 on MINI on CNICS PRO (date xx/xx/yyyy) and is eligible for the CBT4CBT (Computer Based Training for Cognitive Therapy) and APT intervention components. Based on study algorithm and consultation with [name]/ [name] we recommend a prescription of tablet naltrexone 50 mg 1x/day with food. There were no chronic or current opioids listed and no LFTs >5xULN on medical record for this patient (checked on date: xx/xx/yyyy). We have also confirmed with participant about illicit opioid use since naltrexone may interact with opioids.

ARCH IRA study staff: Name

OR

Subject: ARCH IRA study

Pt enrolled to ARCH IRA study: U01 AA020802 - Alcohol Research Consortium on HIV – Intervention Research Consortium

Enrolled on xx/xx/yyyy, with a AUDIT/AUDIT C score of XX

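### In both UAB naltrexone message templates, a current prescribed opioid that is missing from the medical record falls outside the two opioid checks reported

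*Protocol*

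**What the plan says.** Appendix 5 (APT scripts template at UAB, naltrexone prescription) holds two alternative messages from study staff to the treating clinician. Their opioid statements are the same. The first is a record check, with a date field: "There were no chronic or current opioids listed and no LFTs >5xULN on medical record for this patient". The second is a participant check, with no date field: "We have also confirmed with participant about illicit opioid use since naltrexone may interact with opioids".

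The UAB procedure in Section VI.D.i says that staff use the APT algorithm "and the EMR to determine which medication to recommend to the provider". It adds a consultation route: "These recommendations will be done based on APT algorithm plus consultation with PI" or the addiction specialist, case by case. The algorithm itself (Appendix 1, Algorithm 2) is a figure that is not shown. Appendix 2 supplies a reference list headed "Opioid list as prescribed in Cerner at UAB".

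The protocol words its naltrexone exception in the UW notice (Section VI.D.ii). Naltrexone is the usual recommendation unless the patient has serious liver disease "or is currently using prescribed or illicit opioids". At UW, whether a given drug is appropriate "will be assessed by and at the discretion of the patient provider".

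**The concern.** The exception in the UW notice turns on what the patient is currently taking. The record check in the UAB templates turns on what the record lists. These differ for any patient whose opioid was prescribed elsewhere and never entered. The participant question could close that difference, but as reported it is confined to illicit use.

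The stake is patient safety. The message carries the recommendation to the prescriber and gives the interaction as the reason for asking. A prescriber who reads that the record is clear and that the participant has been asked could take opioid use as excluded, although one route was not covered by the question as described. No endpoint, sample size or analysis depends on this.

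**Working it through.** The protocol states no figure to reproduce, so the check is a comparison of wording.

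**Inputs.** The two naltrexone messages in Appendix 5; the UAB procedure in Section VI.D.i; the opioid list in Appendix 2; the UW notice in Section VI.D.ii.

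**Step 1: count the reported checks.** 2 templates × 2 checks = 4, made up of 2 record look-ups and 2 participant questions. Participant questions that cover prescribed opioids: 0 of 2. Since the two templates share the same wording, this count shows that neither template closes the gap. It does not measure risk.

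**Step 2: sort patients by type of current opioid use.**

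| Current opioid | Record check | Participant question as reported | Covered by the exception in the UW notice |
|---|---|---|---|
| Prescribed, on the record | Caught | Not asked | Yes |
| Illicit | Caught only if recorded | Asked | Yes |
| Prescribed, not on the record | Missed by definition | Not asked | Yes |

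The third row is the gap. All three rows fall within the exception, and only the third has no reported check against it.

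**Step 3: ask whether the record could miss a prescribed opioid.** The heading "Opioid list as prescribed in Cerner at UAB" suggests a list built from entries in the UAB system. Several entries, such as "percocet does unknown", look hand-typed and read like reported histories. The record therefore seems to capture at least some outside opioids. That narrows the third row but does not show that it is empty.

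**Step 4: ask whether a later step shown in the protocol closes the gap.**
- Consultation is described for UAB in Section VI.D.i, and the first naltrexone message cites it. The second naltrexone message cites none.
- After prescription, staff counsel on the side effects in Appendix 2. The naltrexone row there, as shown, does not mention opioids.
- The follow-up contact comes one week later, after treatment may have begun.

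These steps lower the risk, but none is described as asking the participant about prescribed opioids.

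**Step 5: size in patients.** This cannot be given. The protocol states neither how many naltrexone recommendations are expected at UAB nor how often a prescribed opioid is missing from the record.

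**The case against.** The strongest reply is that the split is coherent. Prescribed opioids are looked up where prescriptions are recorded, and illicit opioids are asked about because records rarely show them. On that view both halves of the exception are addressed, nothing is contradicted, and a second check on prescribed opioids is only a preference. It is true that there is no contradiction. What remains is that a look-up cannot find what was not entered, and the contact in which to ask already takes place.

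A second reply is that Appendix 5 holds messages, not the screening procedure. Algorithm 2 cannot be seen and may contain a wider question, and a message that omits a question does not prove that it went unasked. This stands and limits the claim to the checks that the templates report. If staff do ask about all opioids, the prescriber is not told so, and the edit would simply record it.

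A third reply is that the risk is already reduced. The message is a recommendation, the attending is copied, the interaction is stated, specialist advice is available and the prescriber decides. This also stands, and it is the main reason that the point is minor.

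A reader might also infer that UW screens more thoroughly than UAB. The protocol does not support that: the UW text states a wider exception but leaves the assessment to the provider. Nor is it a separate fault that the templates do not spell out the participant's answer, since a negative answer is implied by the recommendation.

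**Conclusion.** The point holds as a minor, inexpensive safety improvement, with low-to-medium confidence. In 2 of 2 UAB naltrexone templates, a current prescribed opioid that is not on the record falls outside both reported checks, while the protocol's stated exception covers such a patient.

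This rests on two assumptions: that the templates describe the participant question as it is put, and that the record may be incomplete for opioids from other prescribers. The unseen Algorithm 2 could overturn the first, and the hand-typed list entries weaken the second.

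A reader might go further and infer that patients at UAB would be given naltrexone while taking an opioid. The document does not show this. The prescriber makes the decision, is told of the interaction and can consult, and nothing shows how often the record is incomplete.

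**What to change.** In the participant contact that already takes place, ask about any current opioid use, prescribed by any source or illicit. In both naltrexone templates, replace the sentence on the participant check with:

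*Participant denies current opioid use, prescribed by any source or illicit (asked on date: xx/xx/yyyy).*

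Keep the reminder that naltrexone may interact with opioids, so that the prescriber does not lose it. If the participant reports use, take the case to the consultation described in Section VI.D.i before recommending a drug. Stating the answer and its date gives the participant check the same form as the record check; it is a small gain that comes with the edit.

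The cost is one wider question and one sentence in each of two templates, with no extra visit or staff. If Algorithm 2 already contains the wider question, only the template wording needs to change.

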- Approached refused, not okay to re-approach
- Consented

After selecting the event that best fits your situation, click “Add New Event” in order for it to save.

After consenting a participant for ARCH-IRA and after updating the Protocol History to show “Consented,” a new drop-down will appear for Visit 1. After the participant either completes all or some of Visit 1 or refuses to complete Visit 1, you will update the “Protocol History” with the following options:

Visit 1 drop-down options:

- Withdrawn
- Viewed video 1 Peedy Prime
- Viewed video 1 Peedy Pharma
- Refused video 1
- Refused CBT4CBT
- Refused Pharmacotherapy
- Completed Visit 1

Visit 2 drop-down options:

- Withdrawn
- Eligible – not approached (Video 2)

[figure not shown]
Postpone Video 2
Viewed video 2 Peedy Adherence
Viewed video 2 Peedy Problem
Viewed video 2 Peedy Prize
Refused video 2
Refused CBT4CBT
Refused Pharmacotherapy
Completed Visit 2

APPENDIX 1

Algorithm 1. Overall study algorithm

Algorithm 2. APT algorithm

APPENDIX 2

APT –Medication List

Name	Method	Dosage	Side Effects
Campral (acamprosate)	Tablet	Two 333mg tablets 3x/day with or without food. Some patients may require a lower dose.	
Common side effects: abdominal pain, appetite change, change in sexual desire, diarrhea, dry mouth, gas, itchy skin, nausea, nervousness, prickling or tingling sensation, skin rash, trouble sleeping, vomiting, weakness, weight gain or loss
 
More serious side effects: chest pain, joint pain, pounding or fast heartbeat, symptoms of depression, and thoughts or acts of self-harm
 
Other: Does not help with alcohol withdrawal

Disulfiram (antabuse)	Tablet	250mg or 500mg 2 or 3x/day	
Common side effects: skin rash, mild headaches, metallic taste, mild weakness, dizziness, swollen tongue
 
More serious side effects: allergic reactions (swelling of lips, face) and hives, shortness of breath, seizure, tiredness, yellowing of skin or eyes, dark urine, appetite changes, dizziness, vomiting, weakness, severe diarrhea
 
Other: Produces unpleasant effects if you drink alcohol while taking it

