Atarax Syrup	0.5	Fer-In-Sol Drops	0.2	P.B.Z. Expectorant w/Codeine	
Bactrim Suspension	0.3	Geriplex-FS	18.0	& Ephedrine	6.0
Tr. Belladonna	67.0	Gevabon Liquid	18.0	Quibron Elixir	15.0
Benadryl Elixir	14.0	Kaon Elixir	5.0	Robitussin Syrup	3.5
Bentyl-Pb Syrup	19.0	Kaochlor	3.8	Robitussin AC Syrup	3.5
Benylin Expectorant	5.0	Iberet Liquid	1.0	Robitussin PE	1.4
Brondecon Elixir	20.0	Isuprel Comp. Elixir	19.0	Robitussin DM and Robitussin CF	1.4
Bronkelixir	19.0	Syrup Ipecac	2.0	Rondec DM Syrup and Drops	0.6
Butibol Elixir	7.0	Hydryllin Comp.	5.0	Roniacol Elixir	8.6
Calcidrine Syrup	6.0	Hycotuss Expectorant & Syrup	10.0	Serpasil Elixir	12.0
Cas Evac	18.0	Kay-Ciel Elixir	4.0	Tedral Elixir	15.0
Aromatic Cascara Sagroda	18.0	Lanoxin Elixir Pediatric	10.0	Temaril Syrup	5.7
Carbrital Elixir	18.0	Liquid Lomotil	15.0	Terpin Hydrate Elixir	42.0
Cerose & Cerose DM Expectorant	2.5	Luffylin-GG Elixir	17.0	Terpin Hydrate Elixir w/Codeine	42.0
Cheracol & Cheracol D	3.0	Marax Syrup	5.0	Theo Organidin Elixir	15.0
Choledyl Elixir	20.0	Mediatric Liquid	15.0	Triaminic Expectorant	5.0
Chlor-Trimetone Syrup	7.0	Modane Liquid	5.0	Triaminic Expectorant DH	5.0
Cologel Liquid	5.0	Mellaril Concentrate	3.0	Tussend Liquid	5.0
Citra Forte Syrup	2.0	Mesopin Elixir	12.5	Tussar-2 Syrup	5.0
Coldene Cough Syrup	15.0	Minocin Syrup	5.0	Tussi-Organidin Expectorant	15.0
Conar Expectorant	5.0	Nembutal Elixir	18.0	Tussar SF Syrup	12.0
Coryban D	7.5	Novahistine DH	5.0	Tuss-Ornade Syrup	7.5
Cosanyl DM & Cosanyl Syrup	6.0	Nicol Elixir	10.0	Tylenol Elixir	7.0
Copavin Cmpd Elixir	7.0	Novahistine Expectorant	5.0	Tylenol with Codeine Elixir	7.0
Darvon-N Suspension	1.0	Novahistine Elixir	5.0	Tylenol Drops	7.0
Decadron Elixir	5.0	Novahistine DMX	10.0	Ulo-Syrup	6.65
Dexedrine Elixir	10.0	Nico-Metrazol Elixir	15.0	Valadol Lliquid	9.0
Demazin Syrup	7.5	Nyquil Cough Syrup	25.0	Valpin-PB Elixir & Valprin	5.3
Dilauidid Cough Syrup	5.0	Mol Iron Liquid	4.75	Vita Metrazol Elixir	15.0
Elixir Dimetane	3.0	Organidin Elixir	23.75	Vicks Formula 44	10.0
Dimetane Expectorant	3.5	Ornacol Liquid	8.0	Potassium Chloride Sol.	10.0
Dimetane Expectorant-DC	3.5	Tincture Paregoric	45.0	(Standard)	
Doxinate Liquid	5.0	Parapectolin	0.69	(a no-alcohol solution can be requested)	
Dimetapp Elixir	2.3	Parelexir	18.0		
Dimacol Liquid	4.75	Periactin Syrup	5.0		
Donnatal Elixir	23.0	Pertussin 8 Hour Syrup	9.5		
Donnagel Suspension	3.8	Phenergan Expectorant Plain	7.0		
Donnagel PG Suspension	5.0	Phenobarbital Elixir	14.0		

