Dramamine Liquid	5.0	Phenergan Expect. w/Codeine	7.0		

NOTE:

1. Mouthwashes - Scope, Listerine, Cepacol, Colgate 100, Micrin, all contain approximately 15 - 25% alcohol.
2. All elixirs contain some alcohol.
3. The following anti-tussives do *not* contain alcohol:
 - * Hycodan Syrup
 - * Hycomine Syrup
 - Triaminic Syrup
 - * Tussionex Suspension
 - Orthoxicol Syrup
 - Actifed C Expectorant
 - Omnituss
 - Ipsatol Syrup
4. Other non-alcohol liquids:
 - Chloraseptic mouthwash/gargle
 - Liquiprin (acetaminophen)
 - Dilantin Suspension
 - Alupent Syrup
 - * Noctec Syrup
 - * Vistaril Suspension
 - Antacids
 - Kapoectate and Parget, etc.
 - Sudafed Syrup
 - * Quadrinal Suspension
 - Actifed Syrup
 - Triaminic Syrup
 - Naldecon Syrup
 - Nydrazid Syrup

*Ingestive medications may contain other addictive substances which may be considered.

Courtesy of:
Alcenas Hospital
[name]
[name]

For further information, contact FirstLab's Business Development Department at [contact].

APPENDIX 3

In Person ARCH Recruitment Script:

After your standard introduction...

Based on your answers on the computer/iPad survey you just took, I wanted to talk to you about a research study you might be eligible for today.

The study involves watching a 15-20 minute video about alcohol and how it can affect HIV. There also are additional components of alcohol intervention that may be available during the study; you can make decisions about how much you would like to do.

For patients who watched Peedy video in round 1

While you may have seen a video in the past about your alcohol use, this is a new study that has some additional interventions that may help you with your drinking.

“Are you interested in participating in this study?

If participant responds ‘Yes’ notify recruitment staff to come and proceed with consent process.

If participant responds ‘No’, notify recruitment staff and provide as much detail regarding refusal as you can. Patients who refuse to participate will be informed that this is not a requirement for their care and that their relationship with the 1917 Clinic will not be affected in any way. Ask patient “may we contact you again”. If you receive a definite “NO”, communicate this to study staff and we will not approach this patient in the future. Study staff will make a note of this in the tracking logs and record reasons of decline on the tracking log. The following are the options available for decline:

- Already did Peedy before

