Patient name scored >=4 on MINI on CNICS PRO (date xx/xx/yyyy) and is eligible for the CBT4CBT (Computer Based Training for Cognitive Therapy) and APT intervention components. Based on study algorithm and consultation with [name]/ [name] we recommend a prescription of tablet disulfiram 250mg or 500mg 2 or 3x/day. There were no active prescriptions of ritonavir, tipinavir, metronidazole or any med containing alcohol on medical record for this patient (checked on date: xx/xx/yyyy).

ARCH IRA study staff: Name

OR

Subject: ARCH IRA study

Pt enrolled to ARCH IRA study: U01 AA020802 - Alcohol Research Consortium on HIV – Intervention Research Consortium

Enrolled on xx/xx/yyyy, with a AUDIT/AUDIT C score of XX

Patient name scored >=4 on MINI on CNICS PRO (date xx/xx/yyyy) and is eligible for the CBT4CBT (Computer Based Training for Cognitive Therapy) and APT intervention components. Based on study algorithm we recommend a prescription of tablet disulfiram 250mg or 500mg 2 or 3x/day. There were no active prescriptions of ritonavir, tipinavir, metronidazole or any med containing alcohol on medical record for this patient (checked on date: xx/xx/yyyy).

ARCH IRA study staff: Name

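### The UAB disulfiram templates look for alcohol-containing medications only on the medical record, so products bought without a prescription can be missed

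*Protocol*

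**What the plan says.** Appendix 5 (If Disulfiram Prescription) gives UAB staff two templates, one for use with specialist consultation and one without. Both carry this sentence, followed by a check date: "There were no active prescriptions of ritonavir, tipinavir, metronidazole or any med containing alcohol on medical record for this patient".

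Appendix 2 supplies a product list headed "MEDICATIONS CONTAINING ALCOHOL COMMONLY STOCKED IN MOST HOSPITALS AND PHARMACIES". One entry is "Nyquil Cough Syrup", at 25.0% alcohol. Note 1 under the list adds: "Mouthwashes - Scope, Listerine, Cepacol, Colgate 100, Micrin, all contain approximately 15 - 25% alcohol". Note 3 turns to alternatives, opening with "The following anti-tussives do *not* contain alcohol", and Note 4 names other alcohol-free liquids.

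Section VI.D.i (UAB) says the drug is selected with the APT algorithm and the electronic record, with case-by-case consultation. Once a drug is prescribed, staff talk to the participant "about the side effects of the recommended drug (described in Appendix 2 under medication list". For disulfiram, that medication list says: "Produces unpleasant effects if you drink alcohol while taking it".

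For comparison, both naltrexone templates in Appendix 5 follow their record check with: "We have also confirmed with participant about illicit opioid use since naltrexone may interact with opioids".

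**The concern.** By screening for any alcohol-containing medication and supplying a list of such products, the protocol treats this exposure as relevant to disulfiram. The check it scripts draws on prescriptions or the record, whereas the list covers pharmacy stock in general. A cough syrup or mouthwash that a participant buys personally need not appear on a medical record. The prescriber could then read the template as clearing the patient of alcohol-containing products when only recorded items were examined.

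What is at stake is incidental alcohol exposure in a participant taking disulfiram, including use that begins after the message is sent. Beverage drinking is a separate matter: the prescriber is told the AUDIT or AUDIT-C score and the MINI result, and the medication list already warns about drinking. No endpoint, comparison or sample-size figure is affected.

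**Working it through.** No formula applies to the main claim, so the check sets the texts side by side.

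1. **Reach of the template check.** The sentence can be read in two ways. On the narrow reading, only active prescriptions are searched. On the broad reading, any alcohol-containing medication on the record counts, including recorded non-prescribed items. On both readings the check ends at the record. Neither of the two disulfiram templates reports a question to the participant.

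2. **Reach of the protocol's list.** The list is defined by what hospitals and pharmacies stock, not by what is prescribed. It includes Nyquil Cough Syrup (25.0%), Vicks Formula 44 (10.0%) and Robitussin Syrup (3.5%). The mouthwashes in Note 1 (about 15-25%) may fall outside the template altogether, because it speaks of medications.

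3. **Can the gap be sized?** Counting list entries with a stated percentage, and joining names split over two lines, gives 130. None is marked as prescription or non-prescription. The number that a prescription check would miss could therefore be anything from 0 to 130, and the list does not narrow it. The alcohol percentages describe the products and say nothing about how many the check misses.

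4. **Upper bound on the people concerned.** The planned UAB enrolment is about 259 of 756 participants (259/756 = 34%), and sites may over-enrol. Only those with AUD on the MINI are eligible for pharmacotherapy, and only some of those would have disulfiram recommended. Neither fraction is given, so 259 is a ceiling on planned numbers and not an estimate.

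5. **Does a later step close the gap?** Counselling at prescription draws on the medication list, whose disulfiram entry mentions drinking alcohol but not products that contain it. The one-week follow-up concerns how the participant is doing on the drug and any side effects. Consultation and the prescriber's own judgement may catch an exposure, but no visible text directs anyone to ask about these products or warn of them.

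6. **Comparison with naltrexone.** Both naltrexone templates add a confirmation with the participant about an exposure the record may not show; neither disulfiram template does. This is a precedent within the same set of messages. It is not a contradiction, since the two drugs have different hazards.

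**The case against.** The strongest objection is that the decisive page is not available. Drug selection at UAB runs through Algorithm 2 in Appendix 1, a figure missing from the text at hand, and the templates are messages to a clinician, not the screening procedure. Algorithm 2 may already tell staff to ask. This stands as a limit: a gap in screening cannot be shown, only that the templates do not report such a question. It does not remove the point, because the report to the prescriber and the counselling content remain as described whatever Algorithm 2 contains.

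It can also be said that the template is accurate about what was checked, and that staff already hold a list naming mouthwashes and alcohol-free substitutes, which would serve little purpose for a prescription search alone. That is a fair inference about intent, but no visible instruction tells staff to use the list with the participant.

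The comparator can be called weak: illicit opioids are by definition not prescribed, and the acamprosate templates contain no participant question either. The first part is fair, which is why naltrexone serves only as a precedent. The second carries little weight, because the acamprosate check is a creatinine clearance value, which belongs in the record.

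Finally, disulfiram may be rare. The UW notice says naltrexone is the drug most often recommended, and no frequency or harm can be given. Asking about 130 entries would also be more than one quick question. Both remarks are fair. The first keeps the point minor, and the second is met by asking about classes of product.

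**Conclusion.** The point holds as a minor safety improvement for UAB, worth considering. As written, the disulfiram templates can report a clear check while the participant uses a product on the protocol's own list, such as a 25.0% cough syrup or a 15-25% mouthwash.

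This rests on the assumption that such products are bought without a prescription and are not entered in the record, which the documents do not say. No frequency or size of harm can be derived. The point does not extend to UW, where the provider assesses drug choice, or to UCSD and JHU, whose procedures are still to be determined. Confidence is medium, mainly because Algorithm 2 is not shown.

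**What to change.** - **Before recommending disulfiram at UAB:** ask the participant about non-prescribed alcohol-containing products, by class: liquid cough and cold remedies, elixirs and mouthwashes, with the Appendix 2 list as reference.
- **In both disulfiram templates:** add a line after the record check reporting that the participant was asked and what was answered.
- **In the side-effect counselling at prescription:** add a sentence telling the participant to avoid these products while on disulfiram, which covers use that starts later. Staff can point to the alcohol-free products in Notes 3 and 4, bearing in mind that the asterisk there flags items that may contain other addictive substances.

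The clinical decision stays with the prescriber. If Algorithm 2 already includes the question, only the template line and the counselling sentence are needed. The cost is one short question, one line in each of two templates, and one sentence in a conversation that already takes place.
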